1.1 Synopsis

This randomized placebo-controlled phase 2 study will evaluate whether a two-week exposure to duvelisib, a gamma/delta PI3K inhibitor, reduces inflammation in the lungs in patients with severe SARS-CoV-2 infection and COVID-19 who do not require mechanical ventilation at study initiation. The primary objective of the study is to determine the efficacy of duvelisib treatment in preventing death or the need for mechanical ventilation among patients with WHO-defined severe COVID-19. Key secondary endpoints will be reductions in oxygen requirements of patients and improvements in their performance status, safety and tolerability of duvelisib in the setting of COVID-19, biomarkers of inflammation, and generation of IgG antibody responses to SARS-CoV-2 spike protein. The study will determine if a two-week exposure to duvelisib beginning soon after presentation with severe COVID-19 warrants further evaluation in a larger clinical study.

Title:	Duvelisib Ameliorates Manifestations of Pneumonia in Established Novel Coronavirus Infection (DAMPEN-CI)
Study Description:	This randomized placebo-controlled phase 2 clinical study will evaluate whether a two-week exposure to duvelisib in subjects with severe COVID-19 is safe and well tolerated, and whether exposure to the maximally effective dose of duvelisib will safely and favorably change inflammatory bio-markers and reduce the incidence of the composite end-point of mechanical ventilation or death following the diagnosis of severe COVID-19. We hypothesize that short term exposure to duvelisib in patients with severe COVID-19 will decrease the incidence of mechanical ventilation and death compared with placebo-treated control subjects. We also hypothesize that duvelisib will decrease inflammation and improve time to resolution of symptoms.
Objectives:	
Primary Objective:
 
1) To compare the incidence of the composite end-point of mechanical ventilation or death within 29 days of randomization in subjects with severe COVID-19 given placebo or oral duvelisib 
Secondary Objectives are to compare the duvelisib cohort to the placebo cohort with respect to:
 
2) Days to recovery as assessed by ACTT endpoints as the time to recovery (Day 1 through Day 29) to satisfy one of the following eight categories from the NIAID ordinal scale. The scale is as follows: 1) Death; 2) Hospitalized, on invasive mechanical ventilation or extracorporeal membrane oxygenation (ECMO); 3) Hospitalized, on non-invasive ventilation or high flow oxygen devices; 4) Hospitalized, requiring supplemental oxygen; 5) Hospitalized, not requiring supplemental oxygen - requiring ongoing medical care (COVID-19 related or otherwise); 6) Hospitalized, not requiring supplemental oxygen - no longer requires ongoing medical care; 7) Not hospitalized, limitation on activities and/or requiring home oxygen; 8) Not hospitalized, no limitations on activities.3) Duration of hospitalization4) Death within 29 days of randomization

Protocol Title: Duvelisib A meliorates Manifestations of Pneumonia in Established Novel Coronavirus Infection (DAMPEN-CI)

	
5) ICU transfer within 29 days of randomization6) Incidence of grade III-V adverse events or SAEs (as defined by NCI CTCAE version 5.0)7) Documented secondary bacterial or viral infection within 29 days of randomization.8) Mean frequencies of Th1 and Th17 T cells in blood mononuclear cells at 1, 2 and 4 weeks9) Mean levels of inflammatory serum biomarkers at 1, 2 and 4 weeks10) Gene expression profiles of T cells at 1, 2 and 4 weeks11) Median titers of IgG antibodies to SARS-CoV-2 at 4 weeks
Endpoints:	
Primary Endpoint:
 
1. Composite endpoint of either mechanical ventilation or death within 29 days of randomization 
Secondary Endpoints:
 
2. Days to recovery as assessed by ACTT endpoints as the time to recovery (Day 1 through Day 29) to satisfy one of the following eight categories from the NIAID ordinal scale. The scale is as follows: 1) Death; 2) Hospitalized, on invasive mechanical ventilation or extracorporeal membrane oxygenation (ECMO); 3) Hospitalized, on non-invasive ventilation or high flow oxygen devices; 4) Hospitalized, requiring supplemental oxygen; 5) Hospitalized, not requiring supplemental oxygen - requiring ongoing medical care (COVID-19 related or otherwise); 6) Hospitalized, not requiring supplemental oxygen - no longer requires ongoing medical care; 7) Not hospitalized, limitation on activities and/or requiring home oxygen; 8) Not hospitalized, no limitations on activities.3. Duration of hospitalization4. Duration of hospitalization5. Death within 29 days of randomization6. ICU transfer within 29 days of randomization7. ECOG performance status at day 15 and 29 of randomization8. Incidence of grade III-V adverse events or SAEs (as defined by CTCAE version 5)9. Documented secondary bacterial or viral infection within 29 days of randomization.10. Mean frequencies of Th1 and Th17 T cells in blood mononuclear cells at 1, 2 and 4 weeks11. Mean levels of inflammatory serum biomarkers at 1, 2 and 4 weeks12. Gene expression profiles of T cells at 1, 2 and 4 weeks13. Median titers of IgG antibodies to SARS-CoV-2 at 4 weeks
Study Population:	80 adults aged 18 years or older will be enrolled with severe, confirmed COVID-19
Phase:	Phase 2 randomized, placebo-controlled study
Description of Sites/Facilities Enrolling Participants:	This study will begin at Emory University and will seek to open at one or more secondary site institutions.

[figure not shown]

Protocol Title: Duvelisib Ameliorates Manifestations of Pneumonia in Established Novel Coronavirus Infection (DAMPEN-CI)

Description of Study Intervention:	Duvelisib is an oral PI3K inhibitor that is given at a dose of 25 mg BID
Study Duration:	We estimate that the duration of the study will be approximately 12 months. Participant duration will be approximately 1 month from the time of enrollment

1.2 Schema

Protocol Title: Duvelisib Ameliorates Manifestations of Pneumonia in Established Novel Coronavirus Infection (DAMPEN-CI)

1.2 Schedule of Assessments

Following screening, informed consent, and confirmation that a patient with severe COVID-19 meets all eligibility criteria, subjects will be randomized 1:1 to receive duvelisib 25 mg, po BID or a placebo pill, po BID. Randomization between duvelisib 25 mg po BID and placebo BID will be stratified by study site. The investigational pharmacy will supply coded study drug based upon the results of central randomization.

Procedures and Tests Study Tests DURING HOSPITALIZATION [#]	Days -2 to 0 [@]	Day 1 [@]	Day 8 (± 2)	Day 15 (± 2)	Day 29 (± 3)	Day 50-60
Randomization to duvelisib or placebo arm	X					
Study Drug Administration		Oral drug BID Days 1-14				
SARS-CoV-2 RT-PCR	X					
Immunophenotyping of immune cells in blood		X	X	X	X	
Whole blood for RNA gene expression ^{##}		X	X	X	X	
Mononuclear cells for mass cytometry ^{##}		X	X	X	X	
Plasma cytokines and chemokines ^{##}		X	X	X	X	
Anti-SARS Cov-2 IgG		X			X	
TSH	X				X	
Hepatitis Serologies if known history of treated Hepatitis B or C	X					

Standard of Care Tests*	Days -2 to 0	Day 1	Day 8 (± 2)	Day 15 (± 2)	Day 29 (± 3)	Day 50-60
Physical Exam	X	Performed daily during hospitalization				
ECOG Performance Status	X	Performed daily during hospitalization				
Vital Signs	X	Performed daily during hospitalization				
Clinical Labs: Record data in eCRF (REDCap) during hospitalization as shown below						
CBC with differential	X	Abstract data as available				
CMP	X	Abstract data as available				
Ferritin		Abstract data as available				
CRP, Troponin		Abstract data as available				
Coagulation Tests**		Abstract data as available				
Non-contrast Chest CT or Chest X-Ray	X	Abstract data as available				
Serum or Urine Pregnancy Test***	X					
Assessment of Survival Status						X

study procedures which are performed as part of the research protocol and covered by the study budget

Additional research blood samples will be obtained prior to discharge from hospital

@ Some overlap of procedures and tests performed for screening and Day 1 is expected.

* Standard of care procedures which are routinely performed on COVID-19 patients and the results of which will be recorded as part of study conduct

** PT/INR, PTT, Fibrinogen, D-Dimer, Heparin/Enoxaparin Anti Xa

*** Pregnancy test for WOCBP may be obtained after hospital admission but prior to study enrollment

2. Objectives (and Endpoints)

OBJECTIVES	ENDPOINTS
Primary	
To compare the incidence of mechanical ventilation or death in subjects with severe COVID-19 given placebo or oral duvelisib.	The primary end-point is a composite endpoint of mechanical ventilation or death within 4 weeks of randomization.
Secondary	
Secondary Objectives are to compare the duvelisib cohort to the placebo cohort with respect to:
 
1) Days to recovery as assessed by ACTT endpoints as the time to recovery (Day 1 through Day 29) to satisfy a score of ≥ 5 from the following eight categories from the NIAID ordinal scale. The scale is as follows: 1. Death; 2. Hospitalized, on invasive mechanical ventilation or extracorporeal membrane oxygenation (ECMO); 3. Hospitalized, on non-invasive ventilation or high flow oxygen devices; 4. Hospitalized, requiring supplemental oxygen; 5. Hospitalized, not requiring supplemental oxygen - requiring ongoing medical care (COVID-19 related or otherwise); 6. Hospitalized, not requiring supplemental oxygen - no longer requires ongoing medical care; 7. Not hospitalized, limitation on activities and/or requiring home oxygen; 8. Not hospitalized, no limitations on activities.2) Duration of hospitalization3) Death within 29 days of randomization4) ICU transfer within 29 days of randomization5) ECOG performance status at day 15 and 29 of randomization6) Incidence of grade III-V adverse events or SAEs (as defined by CTCAE version 5)7) Documented secondary bacterial or viral infection within 29 days of randomization.8) Mean frequencies of Th1 and Th17 T cells in blood mononuclear cells at 1, 2 and 4 weeks9) Mean levels of inflammatory serum biomarkers at 1, 2 and 4 weeks10) Gene expression profiles of T cells at 1, 2 and 4 weeks

OBJECTIVES	ENDPOINTS
11) Median titers of IgG antibodies to SARS-CoV-2 at 4 weeks 12) Survival at day 50-60 after randomization	

3. Background

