- EKG as ordered by attending physician
- Labs: Complete Blood Count (includes hemoglobin, platelets, and white blood cell count with differential), Comprehensive metabolic panel (includes sodium, potassium, chloride, creatinine, AST, ALT, total bilirubin, and alkaline phosphatase), ferritin, D-dimer, CRP, troponin (abstract from SOC labs daily or as available), Thyroid Stimulating Hormone (TSH, Day 29)
- Immune phenotyping of leukocytes (days 1, 8, 15, and 29)
- Whole blood for RNA – gene expression analyses (days 1, 8, 15, and 29)
- Mononuclear cells for mass cytometry (CyTOF) (days 1, 8, 15, and 29)
- Plasma for cytokine/chemokine analyses (days 1, 8, 15, and 29)
- Serum for antibodies to SARS-CoV-2 (screening and 29)

Follow-up Phase:

- Survival status on day 50 - 60

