Blood samples for chemistry, hematology, viral serologies, leukocyte immunophenotyping and pregnancy (for pre-menopausal patients) will be analyzed at Emory or secondary site clinical laboratories. The chemistry panel will include sodium, potassium, chloride, bicarbonate, glucose, BUN, AST, ALT, total bilirubin, total protein, ferritin, D-dimer, CRP will be tested at screening and on days 1, 8, 15, and 29. TSH will be tested at screening and at day 29. Hematology panel includes complete blood count, including white blood cell count with differential (neutrophils, lymphocytes, eosinophils, basophils), red blood cell count, hemoglobin, hematocrit and platelet count will be tested at screening and days 1, 8, 15, and 29. Hepatitis viral serologies will be tested at screening if a patient has a prior history of treated hepatitis B or C, and include:

- Hepatitis B Panel (HBsAg, HBsAb, HBcAb and HBV DNA PCR)
- Hepatitis C Panel (HCV Ab and HCV PCR)

Correlative Laboratory Data

- SARS-CoV-2 RT-PCR test from nasopharyngeal swabs will be ordered at screening [baseline, prior to study drug]. Results are returned as positive or negative, with Ct values for positive tests. Note: saliva SARS-CoV-2 PCR test will be added once available.
- Leukocyte immunophenotyping (via flow cytometry/fluorescence-activated cell sorting) will be done at days 1, 8, 15, and 29. This will determine the amount of B/T/NK cells and more specifically, the phenotypes and frequencies of these immune cell populations pre and post duvelisib exposure (Th1 and Th17 T cells).
- Mononuclear cells collected at days 1, 8, 15, and 29 will be stored for CyTOF analyses for more in-depth immune-phenotyping in follow-up studies.
- Blood cells collected at days 1, 8, 15, and 29 will also be collected in RNA stabilization tubes for immunological gene expression analyses.

Protocol Title: Duvelisib Ameliorates Manifestations of Pneumonia in Established Novel Coronavirus Infection (DAMPEN-CI)

- Mean levels of inflammatory serum biomarkers will be measured by ELISA at day 1 [baseline, prior to study drug], during and following 2 weeks of study drug exposure in each cohort, using samples at days 1, 8, 15, and 29
- Median titers of neutralizing antibodies to SARS-CoV-2 will be determined at days 1 and 29.

6. Data and Specimen Banking

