8.1 Duration of therapy and follow up

In the absence of treatment delays due to adverse event(s), subjects will be treated for 14 days with duvelisib/placebo. A subject will be considered to have completed the study if he or she has completed all phases of the study including the last visit or the last scheduled procedure shown in the schedule of activities. Subjects who have signed consent, are deemed eligible and are randomized to receive study drug (duvelisib/placebo) will be considered evaluable for efficacy endpoints on an intent-to-treat basis. Subjects who receive at least one dose of study drug (duvelisib/placebo) will be evaluable for toxicity. The end of the study is defined as completion of the last visit or procedure in SOA (Day 29) and an assessment of survival status on day 50 - 60. In the event of a subject's withdrawal, the Investigator will make every effort to complete the End of Treatment procedures specified in the Schedule of Events. Subjects who withdraw from the study will be encouraged to permit follow-up for clinical end-points, including death, mechanical ventilation (e.g. intubation, high-flow O₂ Bi-PAP or AIRVO), hospital discharge, and need for supplemental oxygenation. Subjects will be assessed daily while hospitalized. If the subjects are discharged from the hospital, they will have phone follow-up calls with a study team member at

Protocol Title: Duvelisib Ameliorates Manifestations of Pneumonia in Established Novel Coronavirus Infection (DAMPEN-CI)

day 15 (window d13 – 25), and at day 29 (window d27 - 39) for clinical outcomes data. Arrangements will be made for an outpatient phlebotomy appointment after day 29 (day 30 - day 60 if possible, but up to day 100) to obtain safety laboratory tests and blood samples for secondary research. Patients will receive \$100 compensation for the in-person follow-up phlebotomy visit. However, travel distance, infection control or other restrictions may limit the ability of the subject to return to the clinic. In such cases, only clinical data will be obtained via the d27 - 39 call.

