At the interim analysis (20 patients/arm), the incidence of death or mechanical ventilation, grade ≥ 3 elevations in liver transaminases, or neutropenia will be estimated. We assume that the underline rate is 40%, 10%, or 24% for the three incidences in placebo group respectively, and if the rate in duvelisib group is $\geq 15\%$ higher than that in the placebo group in either of the three incidences, the trial may be stopped due to the safety concern. It also translates to stop the study if 3 or more excess events in duvelisib group are observed in either of the three incidences. Operating Characteristics, the probability of trial stopping due to ≥ 3 excess events based one simulation study, is listed in the below table.

AEs	Underline event rate in Placebo arm	Underline event rate in Duvelisib arm						
		5%	10%	20%	30%	40%	50%	60%
death or mechanical ventilation	40%	0%	0.02%	0.7%	4.8%	16.6%	37.4%	62.7%
grade ≥ 3 elevations in liver transaminases	10%	0.79%	5.7%	32.8%	65.8%	87.9%	97.2%	99.7%
neutropenia	24%	0.07%	0.6%	7.3%	26.1%	52.7%	77.3%	92.6%

In addition to the study stopping rules based an interim analysis, the Independent Data Monitoring Committee (IDMC) will review, on a monthly basis, the number of Grade 3 and/or Grade 4 adverse events in each arm, including neutropenia and elevated transaminases, and consider stopping or suspending accrual to the study if the frequencies of Grade 3 or Grade 4 adverse events are significantly higher among subjects in the duvelisib arm compared with subjects in the control arm.

Analysis of Safety Data

The primary safety endpoints include death or mechanical ventilation, grade ≥ 3 elvation in liver transminases, and neutropenia within 4 weeks. The cumulative incidence rate of each safety endpoint will be calculated with 95% confidence interval by randomized arms, and compared by Fisher's exact test.

Handing of Missing Data

For the safety endpoints and secondary endpoints, missing data will not be imputed, summaries and analyses will be based on the observed cases. For the primary efficacy analysis, every effort will be made from the informed consent form design to clinical follow up to reduce the missing data. Patients withdraw consent before the primary endpoint can be measured will be replaced.

Demographics and Baseline Characteristics

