All patients who maintain consent to be followed for additional outcome information will remain in the study through the end of the double-blind period collection of safety and efficacy assessments. Subjects discharged from the hospital prior to the last protocol-specified assessment on day 29 will be followed as out-patients with in-person or telehealth visits. Survival status at day 50 - 60 will be captured in all subjects who have not withdrawn consent for follow-up by contacting the patient via a telehealth visit or other approaches (e.g., telephone calls, texts, and emails to the patient and close contacts). In the absence of direct or indirect contact with the subject, a vital records search will be performed to assess survival status of each subject.

Data Retention

All study documents will be retained for at least two years after the last approval of a marketing application in their country and until there are no pending or contemplated marketing applications in their country.

Transmission of Data:

Blood samples for T-cell phenotyping from secondary sites will be cryopreserved and shipped to Emory University in real-time. Patient samples will be cryopreserved by using Crystor Media (please see Appendix F). Emory University will cover the cost of shipment of blood samples. All patient samples for T-cell phenotyping will be analyzed at Emory University to ensure uniform analysis. Clinical data (ORR and rates of CRS, neurotoxicity, ICU

transfers) will be captured with chart review at Emory University and secondary sites. Data will be uploaded into RedCap. There will be monthly meetings (tele-conference) with each site's PI to review the study, enrollment and reporting of data.

Publication Plan

The results of the study should be available within 12 months of completion of the study. The end of the study is the time point at which the last data items are to be reported or after the outcome data are sufficiently mature for analysis. A full report of the outcomes will be made public no later than three years after the end of the study.

16. Provisions to Monitor the Data to Ensure the Safety of Participants

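### Blood counts and chemistry have no firm schedule after screening, and the only outpatient safety draw for discharged patients falls after the 4-week window of the laboratory safety endpoints

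*Combined protocol and SAP*

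**What the plan says.** Three sections describe the same blood tests differently.

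- **Section 1.2, Schedule of Assessments.** CBC with differential and CMP are marked at screening. After that the entry is "Abstract data as available", under the row "Clinical Labs: Record data in eCRF (REDCap) during hospitalization as shown below". The tests are classed as routine standard of care. A footnote adds "Additional research blood samples will be obtained prior to discharge from hospital".
- **Section 5.5, Treatment Phase.** The wording agrees with the schedule: "abstract from SOC labs daily or as available".
- **Section 5.6, Clinical Laboratory Data.** The hematology panel "will be tested at screening and days 1, 8, 15, and 29", and the chemistry panel, including AST and ALT, has the same days. Nothing limits this to inpatients.

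For discharged patients, section 8.1 gives phone calls around days 15 and 29 and an "outpatient phlebotomy appointment after day 29 (day 30 - day 60 if possible, but up to day 100"). If the patient cannot return, only clinical data are taken by phone. Section 15.2 says patients discharged before day 29 "will be followed as out-patients with in-person or telehealth visits", and names no blood tests.

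Section 15.1 sets the primary safety endpoints as death or mechanical ventilation, grade 3 or higher transaminase elevation, "and neutropenia within 4 weeks". The same three outcomes drive the interim safety rule at 20 patients per arm. Missing safety data are not imputed; observed cases are analysed.

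**The concern.** Raised transaminases and a low neutrophil count are often silent, and a phone call cannot find them. If no blood is drawn between discharge and day 29, a new abnormality in that interval is not seen. A patient with normal inpatient results and nothing afterwards would probably still count as observed, and so as a non-event.

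Two of the three interim safety triggers and two of the three primary safety endpoints rest on these tests. The IDMC's monthly review names the same two toxicities. The days off drug matter too. Section 4.2.5 stops study drug at a discharge before day 15, but section 16.2 records adverse events until 14 days after the last dose, and the endpoint runs for 4 weeks regardless.

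A site reading the schedule also cannot tell whether the section 5.6 days are mandatory.

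**Working it through.** **Timing.** Section 15.1 equates 4 weeks with 29 days for the primary endpoint; I assume the same for the safety endpoints. The schedule's day 29 (±3) window covers days 26 to 32. The section 8.1 draw opens on day 30, so only days 30 to 32 overlap. For a discharge on day d, the stretch with no explicitly planned outpatient draw is 29 − d of 28 days: 21 days for d = 8, 14 for d = 15, 7 for d = 22. These are calendar days, not shares of risk.

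**The plan's own figure.** Section 15.1 prints a stopping probability of 65.8% for transaminases at 10% on placebo and 30% on duvelisib (20 per arm, 3 or more excess events). A normal approximation to the difference of two binomial counts gives

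1 − Φ((3 − 20 × 0.20) / √(20 × (0.10 × 0.90 + 0.30 × 0.70))) = 1 − Φ(−1/2.449) = 65.8%.

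That reproduces it. For neutropenia at 24% and 50% the same formula gives 77.3%, as printed. The exact binomial sums are 73.0% and 82.1%. I use exact sums below; the approximation shows a similar fall (transaminases 65.8% to 53.5% at 20% unseen).

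**Equal under-detection.** Let s be the share of true events unseen, the same in both arms, with all 20 patients per arm counted as tested. Each observed rate is the true rate × (1 − s), so the observed difference is (1 − s) times the true one. At s = 20%, 30% against 10% becomes 24% against 8%, and 20 points shrink to 16. The trigger probability is the sum over all pairs with duvelisib events minus placebo events of at least 3.

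| Share unseen, both arms | Transaminases, 30% vs 10% | Neutropenia, 50% vs 24% |
|---|---|---|
| 0% | 73% | 82% |
| 5% | 71% | 80% |
| 10% | 68% | 78% |
| 20% | 62% | 72% |

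**Unequal under-detection.** Take true neutropenia of 24% in both arms, so that any trigger is a false alarm. Full capture gives 18%.

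- 30% unseen on duvelisib, 20% on placebo: observed 0.24 × 0.7 = 16.8% against 0.24 × 0.8 = 19.2%, a spurious −2.4 points; the trigger fires in 11%.
- 20% unseen on duvelisib, 30% on placebo: the reverse, +2.4 points; the trigger fires in 20%.

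The sign of the bias therefore depends on which arm loses more, and the documents do not say.

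**The case against.** The strongest reply is that little is lost. Section 1.2 calls these tests routine, and section 5.5 expects daily results where they exist, so inpatients may be sampled more often than section 5.6 asks. That stands: for inpatients the mismatch is mainly one of wording. Discharged patients are the recovering ones and are off drug, so the share of new silent grade 3 events may be small. At 5% unseen the trigger loses only about 2 points. The rule is also advisory, the IDMC sees grade 3 and 4 events monthly, and section 8.1 names travel and infection control as real limits on return visits. All of this tempers the size; none of it supplies a draw inside the window.

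A reader might infer more than the documents support:

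- *Laboratory follow-up ends at discharge.* Section 5.6 is not restricted to inpatients, section 15.2 permits in-person visits, days 30 to 32 fit the day 29 window, and known adverse events are followed to resolution. What is missing is a planned check for new, silent abnormalities.
- *The safety difference is always understated.* This holds for equal loss. Unequal loss can go either way.
- *Duvelisib patients will have shorter laboratory follow-up.* That requires the drug to shorten hospital stay, which is the trial's hypothesis and not a known fact.
- *The 1.2-month median onset of AST/ALT elevation in section 13 supports the point.* It does not. That is about day 36 (1.2 × 30), outside the 4-week endpoint, and it was seen under longer dosing.

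**Conclusion.** The concern holds in a limited form. Sections 1.2 and 5.5 conflict with section 5.6. For patients discharged before day 29, the only explicitly planned safety draw comes after the endpoint's window, apart from a possible overlap on days 30 to 32. New silent transaminase elevations and neutropenia after discharge can be missed.

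With equal loss of 5 to 20%, the interim trigger loses about 2 to 11 points for transaminases and 2 to 10 for neutropenia. This rests on three assumptions: the share unseen, equal loss in the two arms, and patients with partial results being counted as tested. Section 15.1 does not say how such patients are counted. If they were dropped, the remaining sample would lean towards sicker inpatients and the rates could be overstated.

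These figures describe the loss at assumed shares. They do not measure what the fix recovers. The efficacy endpoint is not affected.

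**What to change.** 1. Make sections 1.2 and 5.5 match section 5.6: require CBC with differential and CMP at the research draws already planned in hospital (days 1, 8, 15 and 29) and at the draw before discharge.
2. Let the section 8.1 outpatient draw open at day 26 and target day 29 (±3) where feasible, using the in-person visits that section 15.2 already allows. Keep the present later window as the fallback when travel or infection control prevents this.
3. Report to the IDMC, by arm, the number of patients with results by days 8, 15 and 29, and the day of each patient's last CBC and CMP.
4. Leave the stopping rule unchanged.

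The cost is a wording amendment and a small laboratory charge, with no extra visit. Research samples taken at the outpatient draw would come earlier. Patients drawn early would have less chance of showing hepatotoxicity that appears after day 32. The interval between discharge and day 29 stays only partly covered: an abnormality that arises and resolves between the two draws is still missed, and some patients will not be able to return.
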